## PATIENT POPULATION, ELIGIBILITY AND ENROLLMENT

Any questions about eligibility criteria must be addressed *prior* to patient randomization. This trial will be conducted in compliance with the master and domain protocols, GCP and Health Canada regulations (as applicable).

### Patient Population

The CORT-E trial is a phase III, multi-centre (30-40 centres), randomized, open-label trial, embedded as a domain within the PRACTICAL platform trial. This domain will enrol patients in the following platform defined states (in both trial cohorts);

[figure not shown]
- Non-intubated patients;
- Intubated patients, not on extracorporeal life support, with low normalized respiratory system elastance (<2.5 cm H2O/ml/kg predicted body weight);
- Intubated patients, not on extracorporeal life support, with high normalized respiratory system elastance (≥2.5 cm H2O/ml/kg predicted body weight);
- Patients on extracorporeal life support.

Patients who satisfy the PRACTICAL platform eligibility criteria **and** the criteria specific to **either** cohort in the CORT-E domain will be considered.

### PRACTICAL Platform Eligibility Criteria

#### PRACTICAL Inclusion Criteria

1. Acute hypoxemic respiratory failure meeting all of the following criteria;
  - a. New or worsening respiratory symptoms developing within 2 weeks prior to the onset of need for oxygen or respiratory support
  - b. Receiving any of the following types of oxygen or respiratory support for at least 4 hours prior to the time of randomization; supplemental oxygen at 10 L/min or higher, high flow nasal oxygen (at any flow rate), invasive ventilator support, extra-corporeal life support (ECLS), or non-invasive ventilator support
  - c. Minimum FiO2 ≥ 0.40 (for venturi mask, high flow nasal cannula, or invasive or noninvasive ventilation) or oxygen flow rate ≥10 L/min on face mask for at least 4 hours at the time of evaluation for eligibility unless already on extra-corporeal life support

2. Age  $\geq$  18 years

#### PRACtical Exclusion Criteria

1. Hypoxemia is **primarily** attributable to acute heart failure or fluid overload
2. Hypoxemia is **primarily** attributable to pulmonary embolism
3. Hypoxemia is **primarily** attributable to status asthmaticus
4. Extubation is planned or anticipated on the day of screening
5. ICU discharge is planned or anticipated on the day of screening
6. The patient is moribund and deemed unlikely to survive past 24 hours (as determined by the clinical team)
7. The patient is being transitioned to a fully palliative philosophy of care

#### **CORT-E2 Domain Eligibility Criteria**

##### **Early Cohort**

##### Inclusion Criteria

1. Within 72 hours of admission to an ICU
2. New unilateral or bilateral airspace disease

[figure not shown]
##### Exclusion Criteria

1. Receiving only low flow oxygen therapy less than or equal to 15L/min
2. More than two doses of corticosteroids (oral or IV, at any dose) received any time during the previous 14 days prior to screening
3. Existing indication for corticosteroids
4. High suspicion for/or confirmed COVID infection
5. Acute traumatic brain injury during the index hospital admission
6. Allergy to dexamethasone

##### **Extended Cohort**

##### Inclusion Criteria

1. Are admitted to an ICU
2. Have already received a short course (defined below) of corticosteroid specifically for acute respiratory failure, this will include patients:

- a. randomized to corticosteroid arm in Early Cohort and completed 10 days of corticosteroid as per Early Cohort protocol
  - b. patients with COVID who have received between 8-12 days of corticosteroids as standard of care
  - c. others who have received between 8-12 days of corticosteroids for AHRF
- OF NOTE: the initial corticosteroid does not have to be dexamethasone and corticosteroids can be at any initial dose
3. Ongoing AHRF requiring HFNC, NIV (continuous positive airway pressure [CPAP] or bilevel) or invasive ventilation

#### Exclusion Criteria

1. An alternate indication for ongoing corticosteroids
2. Acute traumatic brain injury this hospital admission

Eligible non-randomized patients will be identified and reasons for non-enrolment classified as:

1. Lack of consent from patient or substitute decision maker (specifying reason);
2. Refusal from attending physician (specifying reason);
3. Enrolment in a confounding RCT;
4. Research coordinator or drug not available

[figure not shown]
To better characterize the generalisability of our randomized population, baseline, demographic, and outcome data may be recorded on eligible non-randomized patients.

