### **Patient Randomization**

General registration information can be found in the PRACTICAL Master Protocol.

[figure not shown]
Prior to randomizing a patient, each institution must have submitted all necessary regulatory documentation to Ozmosis Research Inc. and received a local activation letter. Access to the eCRFs will be granted once this has been received and randomization will occur online via the REDCap database.

Patient eligibility must be confirmed by the principal investigator or one of the sub-investigators at the site prior to randomization into either cohort in this domain. An explanation of the study, discussion of the expected side effects, and full disclosure of the “informed consent” document must take place. Eligible and consented patients will be randomized into individual cohorts within the domain.

**Early Cohort Screening:** Patients will be screened for eligibility at the time of ICU admission. After-hours screening should be performed where possible, however the 72-hour window for enrolment in the Early Cohort should allow most patients to be captured with weekday screening alone. Patients who do not meet oxygen support thresholds for Cohort #1 at initial screening will be followed to determine if they deteriorate and meet criteria within the 72-hour post-ICU admission window.

**Extended Cohort Screening:** Patients receiving corticosteroids for any type of AHRF in the ICU should be tracked (including patients that are receiving treatment as part of the Early Cohort). Patients that were included in the Early Cohort that remain on treatment for 10 days should be screened for eligibility for a second randomization into the Extended Cohort, and randomized on day 10 of treatment, if eligible. Patients that are receiving their initial course of corticosteroid as part of SOC (and not as part of the Early Cohort), can be screened and if they meet Extended Cohort eligibility criteria after 8-12 days of corticosteroid treatment, they can be approached for consent and possible randomization into the Extended Cohort.

For patients who are receiving their initial course of corticosteroids as part of standard of care and are eligible for the Extended Cohort, randomization into the Extended Cohort should be prioritized at 10 days, or as close to 10 days as possible. However, randomization into the Extended Cohort two days shorter or two days longer are acceptable depending on the initial

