**Extended Cohort**

**Intervention Arm:** Patients randomized to receive extended dexamethasone will receive dexamethasone 10mg for an additional 10 days. At the end of the additional 10 days, the dexamethasone dose will be halved to 5mg for another 5 days (to reduce the risk of adrenal insufficiency) and then stopped (including taper, a total of 23-27 days (depending on the length of their initial course of dexamethasone [8-12 days]) or until ICU discharge or death, whichever comes first). A taper is encouraged, however not mandated even if the patient is sent to the ward. If a patient is discharged from the ICU prior to completing the protocol, then ongoing corticosteroid management will be up to the treating team as per SOC.

Dexamethasone will be administered parenterally (intravenous administration). Specific details on the timing of administration are provided below;

- Dexamethasone is to be administered such that there is no lapse in dexamethasone treatment (no dexamethasone free day in between their last dose from Early Cohort or SOC and their first day of dexamethasone treatment as part of the Extended Cohort).
- If the patient is randomized the day after they received their last dexamethasone dose as part of the Early Cohort or SOC; 10mg dexamethasone will be administered on the day of randomization (Day 0) and this dose will be administered daily for a total of 10 days of treatment (Day 0 – Day 9). Then, the dexamethasone dose will be reduced to 5mg and this dose will be administered daily for a total of 5 days (Day 10 – Day 14).
- If the patient is randomized on the same day they are receiving their last dexamethasone dose as part of the Early Cohort or SOC; 10mg dexamethasone will be administered on the next day (Day 1) and this dose will be administered daily for a total of 10 days of treatment (Day 1 – Day 10). Then, the dexamethasone dose will be reduced to 5mg and this dose will be administered daily for a total of 5 days (Day 11 – Day 15).

**Control Arm:** Those randomized to the comparator arm will stop corticosteroids after their initial course without a taper. All other aspects of care will be directed by the treating team.

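### Dexamethasone allergy excludes patients from the Early Cohort but not from the Extended Cohort, which gives the same drug

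*Protocol*

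**What the plan says.** In the Protocol's domain eligibility criteria, the sixth and last Early Cohort exclusion is "Allergy to dexamethasone". The synopsis lists it in the same place, under the Early Cohort only.

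The Extended Cohort has two exclusions, identical in the synopsis and the eligibility section: "An alternate indication for ongoing corticosteroids" and "Acute traumatic brain injury this hospital admission". The platform exclusions, which apply to both cohorts, number seven and end with "The patient is being transitioned to a fully palliative philosophy of care". None of them deals with allergy.

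The Extended Cohort inclusion criteria give three ways in: completing the Early Cohort steroid arm (2a), COVID with 8 to 12 days of standard-of-care steroids (2b), or any other patient with 8 to 12 days of steroids for acute hypoxemic respiratory failure (2c). A note adds that "the initial corticosteroid does not have to be dexamethasone and corticosteroids can be at any initial dose".

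Under Trial Interventions, Extended Cohort: "Patients randomized to receive extended dexamethasone will receive dexamethasone 10mg for an additional 10 days". A 5 mg taper over 5 days follows. The route is intravenous and no alternative steroid is offered.

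**The concern.** Two cohorts in one domain give the same drug by the same route, and only one of them bars patients who are allergic to it. Following the Extended Cohort criteria exactly would allow a patient with a known contraindication to be randomised to the contraindicated drug.

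The stake is patient safety. There is also a small bookkeeping consequence. A patient kept out because the attending physician objects would be logged as eligible but not randomised. A patient randomised to dexamethasone and never dosed would stay in the intervention arm under intention to treat.

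**Working it through.** There is no figure in the plan to reproduce. The check is whether any written criterion stops a dexamethasone-allergic patient on each route into the Extended Cohort.

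| Route | Screened for allergy in writing? | Already exposed to dexamethasone? | Gap? |
|---|---|---|---|
| 2a, from the Early Cohort steroid arm | Yes, Early Cohort exclusion 6 | Yes, 10 days | No |
| 2b or 2c, first course was dexamethasone | No | Yes, 8 to 12 days | No, in practice |
| 2b or 2c, first course was another steroid | No | Not necessarily | **Yes** |

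1. **Do the Early Cohort exclusions carry over?** No. The Patient Population section asks for the platform criteria plus those of one cohort or the other. The traumatic brain injury exclusion is written out separately in both cohorts, which suggests that shared safety exclusions are meant to be repeated. Allergy was not repeated.

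2. **Can the third row occur?** The inclusion note allows it explicitly. COVID patients are excluded from the Early Cohort, so those on route 2b have not passed its allergy screen. A patient kept out of the Early Cohort by exclusion 6 and then treated by the clinical team with 8 to 12 days of another steroid fits route 2c. A known dexamethasone allergy is also a reason to choose another steroid, so such patients would tend to gather in this row. That last point is inference; the protocol gives no data on it.

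3. **A possible source of the gap.** The Extended Cohort dosing text computes total treatment duration "depending on the length of their initial course of dexamethasone [8-12 days". Read literally, this assumes that every entrant has already had dexamethasone, which the inclusion note contradicts.

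4. **Scheduled exposure of an affected patient in the intervention arm.** 10 days × 10 mg + 5 days × 5 mg = 100 + 25 = 125 mg in 15 daily doses. This is the full schedule: treatment ends at ICU discharge or death, and the taper is not compulsory. It describes what is planned and does not measure allergic harm.

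5. **Illustrative count.** The protocol gives neither an allergy rate nor the share of first courses with another steroid. Assume that 0.1% to 0.5% of the cohort is both allergic and pre-treated with another steroid, and take the stated maximum of 2000 patients.
   - Eligible as written: 2000 × 0.001 = 2, to 2000 × 0.005 = 10.
   - Allocated to dexamethasone at 1:1: 2 ÷ 2 = 1, to 10 ÷ 2 = 5.

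   These counts show an order of size under an assumption and carry no further weight.

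**The case against.** The strongest reply is that actual dosing of a known-allergic patient is unlikely. The trial is open-label, so the treating team knows which drug is to be given. Dexamethasone comes from local hospital supply and is given by ICU nurses. The attending physician may refuse enrolment, and treatment may be stopped at the physician's discretion. The protocol also requires that "Patient eligibility must be confirmed by the principal investigator or one of the sub-investigators at the site prior to randomization", and nothing prevents an investigator from holding back an allergic patient.

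The difference between cohorts also has a plausible rationale. Early Cohort entrants have had at most two steroid doses in the preceding 14 days, while Extended Cohort entrants have had more than a week of steroids. The Master Protocol, pharmacy manual and eligibility form are not at hand and might cover allergy operationally.

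Much of this stands: it makes harm improbable and the number of patients small. It does not make the allergic patient ineligible.

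- Eligibility is confirmed against the criteria, and these omit allergy.
- Refusal by the attending physician is recorded as a reason why an otherwise eligible patient was not enrolled.
- Discontinuation is discretionary and comes after randomisation.
- The patient's own report is a weak safeguard. The Analyses section expects most patients to be unconscious at enrolment, and the Patient Consent section allows deferred consent where the ethics board permits it.
- Prior steroid exposure is reassuring about dexamethasone only if the steroid was dexamethasone.

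The same bedside checks exist in the Early Cohort, and there the protocol still wrote the exclusion down.

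**Conclusion.** The concern holds. As written, a dexamethasone-allergic patient who has had 8 to 12 days of another steroid for respiratory failure is eligible for randomisation to intravenous dexamethasone in the Extended Cohort. The omission is the same in the synopsis and the eligibility section, and it is not a matter that a statistical analysis plan would settle.

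The conclusion rests on the text and does not depend on the illustrative counts. It assumes that no document outside the protocol adds an allergy criterion; the platform exclusions reproduced here do not. Very few patients are likely to be affected, and the effect on power, error rates and estimates is negligible. It should be fixed because it is a preventable safety inconsistency with a trivial remedy.

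**What to change.** Add "Allergy to dexamethasone" as a third Extended Cohort exclusion, in the wording already used for the Early Cohort, in both the synopsis and the eligibility section. Check that the eligibility form for the Extended Cohort carries the same item.

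The cost is one line in two places of an amendment, plus the check of the form. The sample size does not change. Recruitment loss is the same 2 to 10 of 2000 under the assumption above, and these are patients who should not be randomised to the drug in any case.

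In the same amendment, the Extended Cohort dosing text could refer to the initial course of corticosteroid instead of dexamethasone, to agree with the inclusion note.

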#### **Patient Consent**

Patient / substitute decision maker (SDM) (as applicable for patients lacking decision making capacity) consent must be obtained prior to any domain-specific screening procedures, randomization and start of study intervention. Consent process will be conducted as per local REB/IRB requirements and recommendations, Health Canada's notice "Management of Clinical Trials during the COVID-19 pandemic: Notice to clinical trial sponsors", and FDA Guidance on Conduct of Clinical Trials of Medical Products during COVID-19 Public Health Emergency – Guidance for Industry, Investigators.

This requirement may be waived in cases of emergencies when deferred consent is obtained post study intervention, if this is allowable per the site REB. It will be the responsibility of the local participating investigator to obtain the necessary clearance, and to indicate in writing to Ozmosis

Research Inc. that such clearance has been obtained, before the trial can commence at that centre. Sample English consent forms for the trial will be provided. A copy of the initial full board REB/IRB approval and approved consent form must be sent to Ozmosis Research Inc.

### **Patient Randomization**

General registration information can be found in the PRACTICAL Master Protocol.

[figure not shown]
Prior to randomizing a patient, each institution must have submitted all necessary regulatory documentation to Ozmosis Research Inc. and received a local activation letter. Access to the eCRFs will be granted once this has been received and randomization will occur online via the REDCap database.

Patient eligibility must be confirmed by the principal investigator or one of the sub-investigators at the site prior to randomization into either cohort in this domain. An explanation of the study, discussion of the expected side effects, and full disclosure of the “informed consent” document must take place. Eligible and consented patients will be randomized into individual cohorts within the domain.

**Early Cohort Screening:** Patients will be screened for eligibility at the time of ICU admission. After-hours screening should be performed where possible, however the 72-hour window for enrolment in the Early Cohort should allow most patients to be captured with weekday screening alone. Patients who do not meet oxygen support thresholds for Cohort #1 at initial screening will be followed to determine if they deteriorate and meet criteria within the 72-hour post-ICU admission window.

**Extended Cohort Screening:** Patients receiving corticosteroids for any type of AHRF in the ICU should be tracked (including patients that are receiving treatment as part of the Early Cohort). Patients that were included in the Early Cohort that remain on treatment for 10 days should be screened for eligibility for a second randomization into the Extended Cohort, and randomized on day 10 of treatment, if eligible. Patients that are receiving their initial course of corticosteroid as part of SOC (and not as part of the Early Cohort), can be screened and if they meet Extended Cohort eligibility criteria after 8-12 days of corticosteroid treatment, they can be approached for consent and possible randomization into the Extended Cohort.

For patients who are receiving their initial course of corticosteroids as part of standard of care and are eligible for the Extended Cohort, randomization into the Extended Cohort should be prioritized at 10 days, or as close to 10 days as possible. However, randomization into the Extended Cohort two days shorter or two days longer are acceptable depending on the initial

corticosteroid prescription (e.g., if only 8 or 9 days were prescribed) or practicalities (e.g., to avoid weekends or holidays). If there is uncertainty as to whether corticosteroids were prescribed for AHRF or another indication, the treating team should be consulted to confirm eligibility.

Sites will maintain a screening log documenting all patients reviewed and reasons for exclusion.

Eligible and consented patients for either cohort will be randomized via REDCap, following a 1:1 (intervention arm: control arm) schedule stratified by study centre and level of oxygen support (non-invasive, invasive or ECLS) at the time of randomization.

## **STUDY PLAN**

[figure not shown]
### **Study Schedule**

As per the above section, patients will be screened, consented and their eligibility will be confirmed by an investigator prior to randomization.

Patients will receive the study intervention as described in the 'TRIAL INTERVENTIONS' section below.

[figure not shown]
We will collect data on patients during the ICU and hospital stay. The only planned post-ICU discharge follow-up is for vital status (dead or alive) at 60 days and 6 months and for quality of life at 6 months. This will be assessed by monitoring available electronic medical records, obituaries and contacting the patient/family by telephone, if required.

Randomization is Day 0.

**Study Assessment Schema**

Required Investigations*	Baseline	Daily**	D3	D7	D28 or ICU DC 	D60 	6 Months 
Window	Within 72 hours prior to randomization	N/A	N/A	N/A	N/A	+10 days	+/- 14 days
Consent  & Randomization	X						
Demographics 	X						
Medical History 	X						
Vitals 	X	X					
Hemodynamics 	X	X					
Hematology 	X	X					
Biochemistry 	X	X					
Arterial Blood Gases (ABG) 	X	X					
Study Drug Administration	Refer to the 'TRIAL INTERVENTIONS' section for details related to each cohort						
Optional: Blood Sample Collection	X		X	X	X		
Mechanical Ventilation Data		X					
Readiness to Wean	X	X					
Spontaneous Breathing Trial		X 					
EQ-5D-5L							X

Glasgow Coma Scale and Sofa Score	X	X					
Vital Status						X	X
Serious Adverse Events		X 					
Concomitant Medications		X					

 Consent should be done prior to any baseline assessments and according to site institutional timelines. Site should follow their institutional guidelines for consenting window (timeframe for prior to enrollment/protocol treatment). Please refer to section “Patient population, eligibility and enrollment”.

 Demographics include age, gender, height, and weight.

 Hospital admission (date/time), ICU admission (date/time), APACHE IV, Charlson Comorbidity Index, COVID-19 infection status

 Vitals include temperature, heart rate, respiratory rate, and blood pressure.

 Hemodynamics include BP, PCWP, SvO2

 If multiple time points for baseline data are available within the time point window, values closest to randomization should be entered.

 Hematology reporting on Hg, WBCs, and platelets.

 Biochemistry will include reporting the following values: sodium, glucose, creatinine, albumin, bilirubin, potassium, bicarbonate.

 ABG testing will include the following parameters: pH, PaCO2, HCO3, SaO2, lactate, hemoglobin.

 Spontaneous breathing trials will be conducted only when patient is deemed ready for weaning and per standard of care and/or institutional guidelines.

 SAEs will be reported at the start of randomization and for a period of up to 30 days, or while in ICU, whichever is shorter.

 EQ-5D-5L administered via phone or e-mail at 6 months.

[figure not shown]
 The timing of the D60 and 6 Month follow-up are based on calendar days from the day of randomization (D0). The second randomization date (Extended Cohort randomization) will be used as the starting point for this follow-up for patients randomized into both the Early Cohort and Extended Cohort. These patients do not have to have these follow-up assessment’s done twice.

 The Day 60 vital status check can be done based on review of medical records if the site has access. In those cases, it is not necessary to contact the patient.

 Day 28 or ICU discharge (DC) (whichever is sooner)

[figure not shown]
\*All highlighted and blue fields are standard-of-care assessments and data being collected for study purposes.

\*\*Daily data common to all groups will be collected for the duration of ICU stay and up to day 30 (no daily data will be collected on the ward).

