#### Secondary Outcomes

1. Mortality at other endpoints (ICU/hospital discharge, 30 days and 6 months)
2. Hospital length of stay
3. Duration of NIV
4. Duration of supplemental oxygen use
5. Ordinal scale of daily respiratory support\*\*
6. Need for ECLS
7. Duration of ECLS (for those that require ECLS)
8. Ventilator-free days (VFDs) censored at day 30
9. Health-related quality of life at 6 months (measured with EQ-5D)
10. *Complications from Corticosteroids:*
  - a. Hyponatremia (serum sodium > 150 mmol/L)

- b. Hyperglycemia (requiring new insulin or increase in insulin by >30% from initial/baseline dose)
- c. Delirium
- d. Clinically important GI bleeding (requiring endoscopy or RBC transfusion)
- e. Nosocomial infection
- f. Neuromuscular weakness

\*\*The daily respiratory support ordinal scale will use longitudinal proportional odds to categorize each patient's daily respiratory support needs for 30 days. Each patient will be assigned one of the following ordinal categories each day: 6 (no support), 5 (supplemental oxygen), 4 (high flow nasal cannula), 3 (non-invasive ventilation), 2 (invasive mechanical ventilation), 1 (extracorporeal life support), 0 (death). We will assess daily respiratory support needs using Markov longitudinal proportional odds modelling to estimate an odds ratio. This represents a novel scale that will be assessed compared to the other patient-important outcomes listed above.

---

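### The 30-day daily respiratory support scale needs a category for every patient on every day, but daily data stop at ICU discharge, so later days have no data source

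*Protocol*

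**What the plan says.** Under Secondary Outcomes, the note on the ordinal scale covers "daily respiratory support needs for 30 days" and states: "Each patient will be assigned one of the following ordinal categories each day". The categories run from 6 (no support) and 5 (supplemental oxygen), through high flow nasal cannula, non-invasive ventilation, invasive ventilation and ECLS, to 0 (death). The analysis is a Markov longitudinal proportional odds model that yields an odds ratio. Nothing in the note confines the scale to days in the ICU. The same list contains "Duration of supplemental oxygen use", with no ICU limit, no horizon and no further definition.

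The note on daily data under the Study Assessment Schema reads: "Daily data common to all groups will be collected for the duration of ICU stay and up to day 30". It then adds in parentheses that "no daily data will be collected on the ward".

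The Study Schedule section opens with a general statement, "We will collect data on patients during the ICU and hospital stay", and continues: "The only planned post-ICU discharge follow-up is for vital status (dead or alive) at 60 days and 6 months and for quality of life" (the latter at 6 months).

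The section on minimizing bias states that neither patients nor treating staff are blinded.

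**The concern.** The outcome definition and the collection rule do not fit together. The scale needs 30 daily states per patient, and collection supplies states only while the patient is in the ICU. The states lost are mainly the two best ones, no support and supplemental oxygen, together with any high flow or non-invasive support given on a ward.

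Two things are at stake. First, the scale cannot be completed as the protocol defines it, yet the protocol presents it as a novel measure to be assessed against the other patient-important outcomes. Second, the point at which observation stops is neither fixed nor random. It is a clinical decision linked to the patient's respiratory status and made by people who know the allocation. If discharge practice differs between arms, the pattern of missing days differs too. Oxygen duration has the same weakness if it is taken from ICU records only.

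**Working it through.** No figure in the protocol is in dispute. The check sets the sections side by side and then illustrates the size.

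**Step 1: what the ordinal outcome requires.** One category per patient per day for 30 days, in or out of the ICU (Secondary Outcomes).

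**Step 2: what is collected.** Daily data during the ICU stay, capped at day 30, and none on the ward (Study Assessment Schema). After ICU discharge, the named follow-up is vital status at 60 days and 6 months and quality of life at 6 months (Study Schedule).

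**Step 3: what is left for days after ICU discharge.** Death (category 0) can be placed on the right day only if a date of death is recorded; the Study Schedule describes vital status as dead or alive. Categories 6 and 5, and categories 4 or 3 if that support is given on a ward, have no stated source. The protocol gives no rule for assigning a category on these days.

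**Step 4: size for the ordinal scale.** The protocol gives no ICU length of stay, so the discharge day d is an assumption. Counting 30 daily states, with those up to day d observed:

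share unobserved = (30 − d) / 30

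| Assumed ICU discharge day d | Unobserved days | Share of 30 |
|---|---|---|
| 7 | 23 | 77% |
| 10 | 20 | 67% |
| 14 | 16 | 53% |
| 20 | 10 | 33% |

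These shares apply to a patient who is alive at discharge and for whom nothing later is recorded. Dated deaths would fill in some of the days.

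**Step 5: size for oxygen duration, if recorded in the ICU only.** Suppose there is no true difference in oxygen need, a share p of patients leaves the ICU still on oxygen, and one arm is discharged one day earlier. Then:

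artificial difference = p × 1 day

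For p = 0.3 this is 0.3 days; for p = 0.7 it is 0.7 days. Both p and the one-day shift are assumptions chosen to show scale.

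**Step 6: whether the loss can be ignored.** A Markov model conditions on the previous state, so fewer observed days do not by themselves bias the transition odds ratio. Bias arises if discharge depends on current or expected status beyond the recorded state and covariates. That is plausible, because patients leave the ICU as support is stepped down and the first state after discharge is never seen. The protocol's content does not allow the sign or size of such a bias to be derived.

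**The case against.** The strongest reply has five parts.

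*The Study Schedule says data are collected during the hospital stay as well.* It does, and some hospital data must be captured, since hospital length of stay and mortality at hospital discharge are listed outcomes. Those need only dates, however. The sentence names no respiratory item, the next one narrows it, and the schema note rules out daily ward data in terms. It is a further inconsistency to reconcile and does not supply the missing states.

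*Oxygen duration needs only a start and a stop date.* This stands. The outcome is named without a definition, and the schema is not a full list of fields: it also has no row for hospital length of stay, delirium or nosocomial infection. The missing stop-date row therefore proves little. A reader might infer that oxygen duration cannot be computed at all; the document supports only that it is truncated at ICU discharge unless a stop date is captured.

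*The statistical analysis plan may state the rule for days after discharge.* It may, and it is not at hand. But a rule can only assume a state; it cannot recover support that was never recorded.

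*The bias is not shown.* This stands as to direction. A reader might infer that the arm leaving the ICU sooner is penalised because it contributes fewer of its best days, so that the odds ratio could point the wrong way. Nothing in the document establishes that, for the reason given in step 6.

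*The magnitude is assumed.* Also correct. No single percentage should be read as the trial's expected loss.

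**Conclusion.** The point holds for the ordinal scale: a fixed outcome definition and a fixed collection rule contradict each other. Followed as written, the plan has no data source for the scale after ICU discharge, apart from death if dated. The illustrative loss is 33% to 77% of the 30 days and rests wholly on an assumed discharge day between 20 and 7.

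For oxygen duration the point is conditional on no stop date being captured. Any ward-based non-invasive ventilation, and ventilation after ICU discharge that would count towards ventilator-free days to day 30, share the gap to a smaller degree.

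The loss may be informative and may differ by arm because discharge is an open-label decision, but neither its direction nor its size is established. It would also go too far to say that the model will be fitted to ICU days only, since no section says so.

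The primary outcome and the stopping triggers, which use 60-day mortality, are unaffected. This should be corrected, but it does not threaten the trial's main conclusion.

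**What to change.** **Preferred.** Amend the daily data note in the Study Assessment Schema, and reconcile the Study Schedule text with it, so that two items are abstracted from the chart until hospital discharge or day 30: the highest respiratory support on each day, and the date supplemental oxygen stopped. State which category applies between hospital discharge and day 30, and record the date of death. The cost is a small amount of extra chart abstraction, one field per ward day plus the dates.

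**If ward data will not be collected.** Redefine both outcomes under Secondary Outcomes as ICU-based. Give an explicit rule for days after ICU discharge, record ICU readmission and death dates so that the rule can be applied, and add a sensitivity analysis to that rule. State the limitation that ICU discharge is an open-label decision. This costs less to collect but is more than a wording change, because it needs dates that the Study Schedule does not list. It also loses information on ward support. Simply scoring everyone alive and out of the ICU in the best state would be a poor rule: the unblinded discharge decision would then set the outcome directly, and a patient on high flow or non-invasive support on a ward would score as fully recovered.
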